- **3) Web intervention with minimal face to face support.** This group aims to provide a very brief intervention with minimal face to face contact time which therefore could be applied more rapidly and extensively in the NHS. Patients will work through the website, will be prompted to use it regularly by email, and brief face to face contact for weighing only at 6 and 12 months as in the control group. In addition this group will have a brief (10 min) face to face consultation at 2 weeks to confirm the physical activity and dietary targets, 3 brief online contacts at 1, 2, and 3 months and up to 2 further telephone contacts (i.e. 3 brief additional personal contacts compared with the control group until final follow-up) for patients not losing 5% of weight.

Support and training for Nurses. We have shown in piloting that nurses can learn to use the structured intervention materials both easily (i.e. requiring relatively little training) and effectively. The web pages for nurses a) provide a brief overview of the rationale, philosophy and structure of the intervention, b) provide a structured guide to the content of each patient support session c) give nurses access to an overview of their patients' progress and the content of each session, and d) send email reminders and notifications to nurses when patient support sessions are required (at timed intervals and if patient not using website or not losing weight), and include a tick-box record for nurses to complete logging what support has been provided.

Proposed time period for retention of relevant trial documentation

Trial documentation will be kept for 15 years.

Proposed outcomes/data collection (at baseline and unless specified at 6 and 12 months). Primary outcome measure:

Weight (primary outcome): lightly clothed, without shoes, at the same time each day, and using automated Tanita digital scales (which will also allow measurement of body composition).

Secondary outcome measures:

Food and drink consumption and physical activity (at baseline and final follow-up): These behavioural measures (and intentions/attitudes to behaviour – see below) will be made in the intervention group at baseline and follow-up but in the control group only at final follow-up to avoid

such measurement being a prompt for behaviour change in the control group.

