Adherence and predictors of adherence. We will measure intention to change behaviour for each specific behaviour, and other items based on components of the TPB⁵⁶ (attitudes, social norms, perceived behavioural control) ^{2;15;16} ⁵⁶. We will measure behavioural adherence through self report which is likely to strongly predict weight loss³⁵. All website usage is automatically recorded, including frequency and duration of logins, options selected and all data inputted (e.g. weekly goal achievement).

Outcome measurement: At the appointments with the practice nurse (baseline, 6 months, 12 months), the physiological measurements will be performed, and patients weighed; research staff blind to group will also perform a final weight measurement at 12 months. For the few patients who do not provide questionnaire answers we will perform up to 2 emails/mailings, and telephone follow-up of those still not responding.

Socio-Demographic data. Age, gender, education, internet experience, social deprivation indices based on post code will be recorded.

Notes review. All patient's notes will be reviewed to document consultations, returns, time to return, reasons for returns, complications, economic data and any subsequent referrals. ⁵⁷

Sample size. We wish to compare each of the intervention groups primarily with control but also with each other so for our primary outcome (weight) we allow for alpha=0.017 (i.e. 0.05/3) to minimise type I error. For a standardised effect size of 0.33 (i.e. a small effect size, equivalent to 2-3 Kg difference assuming an SD of change of 6.5-7.5 Kg^{6,48}) and 80% power this requires 174 patients per group with complete data, or 654 patients in total allowing for 20% loss to follow-up (hence we will aim to recruit a minimum of 660 patients).

Analyses

Primary analysis: Repeated measures ANOVA for the principal continuous outcomes (i.e. weight) between groups and for the secondary outcomes, controlling for stratification variables.

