Web + Nurse support	weight, waist, height, bodyfat, blood pressure, Liver function test; fasting serum cholesterol / HDL / LDL/triglyceride(TG), glucose, Hb1Ac and insulin; ferritin	weight, waist, height, bodyfat, blood pressure, Liver function test; fasting serum cholesterol / HDL / LDL/triglyceride(TG), glucose, Hb1Ac and insulin; ferritin	weight, waist, height, bodyfat, blood pressure, Liver function test; fasting serum cholesterol / HDL / LDL/triglyceride(TG), glucose, Hb1Ac and insulin; ferritin	
	EQ-5D, FFQ, Godin, SF36, sociodemographic Q, patient satisfaction and understanding Q, HAD EQ-5D, Godin, SF36, patient satisfaction and understanding Q, HAD		EQ-5D, FFQ, Godin, SF36, patient satisfaction and understanding Q, HAD	
	Attitudes & Intentions baseline Attitudes & Intentions mid- trial		Attitudes & Intentions post trial	
	Motivation to take part Q	PETS adherence mid-trial	PETS Adherence	
Web + minimal support	weight, waist, height, bodyfat, blood pressure, Liver function test; fasting serum cholesterol / HDL / LDL/triglyceride(TG), glucose, Hb1Ac and insulin; ferritin bodyfat, blood pressure, Liver function test; fasting serum cholesterol / HDL / LDL/triglyceride(TG), glucose, Hb1Ac and insulin; ferritin bodyfat, blood Liver function test; fasting serum cholesterol / HDL / LDL/triglyceride(TG), glucose, Hb1Ac and insulin; ferritin		weight, waist, height, bodyfat, blood pressure, Liver function test; fasting serum cholesterol / HDL / LDL/triglyceride(TG), glucose, Hb1Ac and insulin; ferritin	
	sociodemographic Q, patient satisfaction and patient satisfaction and sati		EQ-5D, FFQ, Godin, SF36, patient satisfaction and understanding Q, HAD	
	Attitudes & Intentions baseline Attitudes & Intentions midtrial		Attitudes & Intentions post trial	
	Motivation to take part Q	PETS adherence mid-trial	PETS Adherence	
Normal Care	weight, waist, height, bodyfat, blood pressure, Liver function test; fasting serum cholesterol / HDL / LDL/triglyceride(TG), glucose, Hb1Ac and insulin; ferritin	weight, waist, height, bodyfat, blood pressure, Liver function test; fasting serum cholesterol / HDL / LDL/triglyceride(TG), glucose, Hb1Ac and insulin; ferritin	weight, waist, height, bodyfat, blood pressure, Liver function test; fasting serum cholesterol / HDL / LDL/triglyceride(TG), glucose, Hb1Ac and insulin; ferritin	

[figure not shown]
EQ-5D, sociodemographic Q,	EQ-5D,	EQ-5D, FFQ, Godin, SF36, patient satisfaction and understanding Q, HAD

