		Attitudes & Intentions post trial
		PETS Adherence

POWER Phase 1: Web development 0-12 months RECRUITMENT FLOWCHART

Web site developed, building on previous websites and materials used in Counterweight programme

Phase 2: RCT 12-24 months RECRUITMENT FLOWCHART AND OVERVIEW

Phase 2 (RCT) - DETAILED OUTLINE OF RECRUITMENT AND PARTICIPATION

Identification of participants		Letters sent by practice to potential participants with PIS
Interested participants		Interested participant asks to see Practice Nurse about study Interested participant discusses study details with GP or nurse Interested participant can contact study team to discuss study
Consent		GP or nurse answers any queries the potential participant may have and takes informed consent
		Nurse answers any queries the potential participant may have and takes informed consent
Baseline measures		Practice nurse completes baseline assessment
Baseline questionnaires		Patient completes baseline questionnaires on-line
Randomisation		Research team contacts external randomisation service
Notify participant of random allocation		Research team contacts participant and practice to inform them of allocation
Randomisation options	A B C	Minimal face-to-face support (1 follow up after 2 wks + 3 online contacts (1m,2m&3m) and up to 2 further phone Intensive (face to face visits at 2wks, 6wks & 3m, then up to 4 extra face to face contacts) Normal care
6 month follow up data collection	A, B, C	Appointment made with practice nurse
12 month follow up data collection	A,B, C	Appointment made with practice nurse, validation of final weight by research nurse
Notes review	A B, C	Completed by practice or research team

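### The baseline questionnaires differ by arm but are scheduled before randomisation, and the repeated measures analysis set for secondary outcomes cannot be run against control for six questionnaire measures

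*Protocol*

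**What the plan says.** **Default timing.** The outcomes section of the protocol opens with a general rule: "Proposed outcomes/data collection (at baseline and unless specified at 6 and 12 months".

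**Exception.** Under Secondary outcome measures, food and drink, physical activity and intentions/attitudes "will be made in the intervention group at baseline and follow-up but in the control group only at final follow-up". The reason given is to avoid "such measurement being a prompt for behaviour change in the control group".

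**Table 1.** At baseline the two web arms complete EQ-5D, FFQ, Godin, SF36, socio-demographics, satisfaction, HAD, attitudes and a motivation questionnaire. The Normal Care row has only "EQ-5D, sociodemographic Q" at baseline and EQ-5D at 6 months. All three arms complete the full outcome battery at 12 months.

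**Order of events.** The detailed outline for Phase 2 lists the practice nurse's baseline assessment, then "Patient completes baseline questionnaires on-line", then "Research team contacts external randomisation service", then notification of allocation. No row before randomisation is split by arm.

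**Analysis.** Repeated measures ANOVA is prescribed for weight "between groups and for the secondary outcomes, controlling for stratification variables". The Subgroup analyses paragraph adds analyses by change in components of the theory of planned behaviour (TPB).

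**The concern.** Three parts of the protocol do not fit together.

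- **Schedule.** A battery that depends on the arm cannot be given before the arm is known. The protocol does not say whether controls also complete it or whether web patients complete it after allocation. The second choice means that the web arms' baseline may already reflect knowledge of the allocation.
- **Text against table.** Table 1 withholds three more questionnaires from controls than the text does, and gives no reason.
- **Analysis against data.** The method fixed for secondary outcomes needs at least two occasions in each arm. For several of them, controls have one.

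At stake are the secondary comparisons with control on diet, activity, quality of life, mood, satisfaction and attitudes. If baselines are not collected, they cannot be recovered after recruitment. There is also unequal measurement: by the protocol's own reasoning these questionnaires may prompt behaviour change, and only the web arms receive them early.

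**Working it through.** **1. Schedule by arm** (Table 1, set against the exception under Secondary outcome measures)

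| Measure | Web arms: baseline / 6 m / 12 m | Control: baseline / 6 m / 12 m | Covered by the text's exception? |
|---|---|---|---|
| FFQ | yes / no / yes | no / no / yes | yes |
| Godin | yes / yes / yes | no / no / yes | yes |
| Attitudes and intentions | yes / yes / yes | no / no / yes | yes |
| SF36 | yes / yes / yes | no / no / yes | **no** |
| HAD | yes / yes / yes | no / no / yes | **no** |
| Satisfaction | yes / yes / yes | no / no / yes | **no** |
| EQ-5D | yes / yes / yes | yes / yes / yes | not needed |
| Weight and physiological measures | yes / yes / yes | yes / yes / yes | not needed |

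Six measures lack a control baseline. For three of them the default rule requires one. The text's exception also covers physical activity measured by activity monitors, which Table 1 does not list.

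**2. Can the schedule be followed?** The outline's order is assessment, questionnaires, randomisation, notification. Two readings are possible:

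- Everyone completes the battery before randomisation. This contradicts the exception and the Normal Care row of Table 1, and loses the aim of not prompting controls.
- Only web patients complete it. This contradicts the outline's order, and the values are then taken after randomisation, perhaps after notification.

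No reading satisfies all three places.

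**3. Can the analysis be run?** A repeated measures comparison with control needs the control group's change over time. With control values at 12 months only, that change cannot be estimated for the six measures. Nor can change in TPB components be computed in controls. The 12-month difference between arms, adjusted for the stratification variables, can be estimated.

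**4. What the missing control baseline costs.** The protocol gives no power figure for these outcomes, so this is an illustration.

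- Completers per arm: 660 × 0.8 / 3 = 176 (Sample size: 660 recruited, 20% loss, three groups).
- Difference 0.33 SD and alpha 0.017, both borrowed from the weight calculation; alpha is taken as two-sided (assumption).
- Baseline-to-12-month correlation r: not in the documents; assumed 0.3, 0.5, 0.7.
- Residual variance after baseline adjustment: 1 − r². Power = Φ(0.33 × √(176/2) / √(1 − r²) − z), where z is the two-sided 0.017 critical value.

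| Analysis | Variance relative to adjusted analysis | Power |
|---|---|---|
| 12-month values only | see rows below | 76.1% |
| Adjusted, r = 0.3 | 1/(1 − 0.09) = 1.10 | 80.5% |
| Adjusted, r = 0.5 | 1/(1 − 0.25) = 1.33 | 88.3% |
| Adjusted, r = 0.7 | 1/(1 − 0.49) = 1.96 | 97.4% |

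The middle column is the factor by which variance is larger without the baseline.

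**The case against.** **The asymmetry is deliberate.** The protocol states why controls are spared the behavioural measures. That is a legitimate trade-off, and its wish to avoid prompting controls is not an error. But the reason does not reach SF36, HAD or satisfaction, and it does not settle when the web arms complete theirs.

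**The outline is only an outline.** The conflict depends on reading its rows as time order, and the narrative on randomisation does not place questionnaires before allocation. Nothing elsewhere gives a different order, however, so the places still need reconciling. Table 1 is partly broken in the copy read, but its Normal Care row is legible and agrees with the text on the behavioural measures.

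**A reader might infer that comparison with control is impossible.** The documents do not support this. Every arm has a 12-month value, randomisation makes that comparison valid, and the only covariates named are the stratification variables. A mixed model would accept controls with one occasion, but against control it then informs only the 12-month difference. What is lost is the repeated measures form, baseline adjustment and a check of baseline balance.

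**A reader might also shrink the sample size,** arguing that at r = 0.5 to 0.7 the 174 per group is worth only 174 × 0.75 = 131 to 174 × 0.51 = 89 with adjustment. That number was set for weight, which has all its baselines. No power is claimed for the questionnaires, the correlation is assumed, and the protocol does not name baseline scores as covariates.

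**A reader might conclude that the effect on weight is biased by measurement.** The protocol's reasoning allows for such an effect but gives no size. The website already asks web users for their weight and goal achievement in every session after the first, so any addition from the questionnaires is unknown and may be small.

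**Conclusion.** The point holds for the secondary questionnaires, at the level of should fix. The schedule cannot be followed as listed, text and Table 1 disagree on three instruments, and the prescribed analysis cannot be run against control for six measures. Comparisons at 12 months stay valid, but they estimate the web package together with its extra measurement. On the assumptions above, the loss of precision runs from slight (variance 1.10 times larger at r = 0.3) to substantial (1.96 times at r = 0.7).

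Weight, physiological measures and EQ-5D keep their baselines in all arms. Web-versus-web comparisons keep theirs too, provided the questionnaires were completed before the allocation was known. The primary analysis is not called into question here.

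**What to change.** 1. **Reconcile** the exception under Secondary outcome measures, Table 1 and the Phase 2 outline. State which questionnaires are completed before randomisation, identically in all arms, and which after allocation. Say explicitly whether satisfaction is exempt for controls.
2. **Collect SF36 and HAD in all arms** before randomisation and at 6 months, as the default rule already implies.
3. **Change the analysis** for outcomes without a control baseline. Replace repeated measures ANOVA against control by a 12-month comparison adjusted for the stratification variables and for baseline variables measured in all arms. Use no web-only or post-allocation baseline in a comparison with control. Such values may serve between the two web arms, which share a schedule, if completed before the allocation was known. If controls remain without baseline attitudes, state that change in TPB components is analysed in the web arms only.
4. **If behaviour and attitude measures are still given early to the web arms only,** report them as part of the web intervention package, since the protocol itself regards them as a possible prompt.

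The cost is protocol wording, online questionnaire set-up and two more questionnaires for controls at two visits. The behavioural measures would still have no control baseline. That is the price of the protocol's choice not to prompt controls, and it should be stated.

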Following the completion of all nurse support appointments, practice staff with experience of recruiting and/or supporting patients recruited to the study will be invited to take part in an interview in order to understand their experiences of delivering the study and working with patients in the study. Views about the website and the study procedures will be sought in order to improve our understanding of the deployment of the programme within primary care and inform future programme development.

Phase 2. RCT

Inclusion criteria. Adult patients with BMI >=30 (or 28 with hypertension or hypercholesterolaemia) documented in the GP case records¹² will be eligible.

Exclusions: Current major mental problems e.g. psychosis (difficulty completing outcomes); very ill or unable to change diet (e.g. severe LVF); pregnancy, or breast feeding; perceived inability to walk 100 metres (physical activity difficult).

Invitation of patients/recruitment. Up to 100 patients in each practice will be randomly chosen from GP electronic records, and invited by letter to a screening appointment to confirm eligibility; with 15-20 patients per practice being recruited to the trial. Patients can also be referred opportunistically when seen in practice nurse or GP clinics. Recruitment will take place over 6 months in up to 44 practices from the South West and South East Hubs of the PCRN.

Randomisation and informed consent. At the screening appointment the practice nurse will take written, informed consent and the patients' details in each practice will be sent to an external randomisation line to allow stratification of randomisation - gender; waist (>102 cm men; >88cm women); BMI >=35; Index of material deprivation score (>median); partner in the household; source of patients (invited by mailing or opportunistically invited). Practice staff will inform patients of their group indicating the nature and timing of contacts (and with the personalised website password as appropriate in the web group).

Planned interventions

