
- reinforced by pedometer use⁸, or setting personal physical activity goals. The patient can select all subsequent weight loss sessions from a menu which includes coverage of healthy drinking patterns, relapse prevention, and coping with cravings, stress-induced eating, busy times and social pressures.
- Nurse support. Very brief appointments for weight measurement at 6 months and 12 months (final follow-up) will occur as in the control group. In addition all patients will be offered brief face to face behavioural assessments at 2 weeks, 6 weeks, and 3 months. If a rate of weight loss equivalent to 5% weight loss over 6 months is not being achieved or maintained which we anticipate could be up to half the cohort face to face appointments will be made, up to a maximum of 4 more appointments in total in the first year (which is half the number of the average face to face appointments for dietary and behavioural counselling from trials documented in the NICE review⁵). In line with NICE guidance⁵ if 5% weight loss in not achieved Orlistat will be offered; it will be stopped according to standard stopping rules ⁵. Orlistat can also be used for weight maintenance⁵. The purpose of the nurse contacts is to provide reinforcement, and also to be able to help patients address ongoing or new issues where the web has provided limited support. Where issues arise the approach will be to encourage patients to find their own solutions to the problems raised.
- Other features. Based on previous evidence from systematic review of particular strategies to encourage maintenance of weight loss¹¹, patients will asked to participate in web based peer interaction, and to involve the family or spouse to help limit weight regain.

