Physical activity: Using the validated Godin leisure time physical activity questionnaire and physical activity monitors^{29,30}. Activity monitors have well documented limitations in validity, although may provide an adequate proxy to estimate between group differences. One third of the sample will in addition be randomised to wear the Actiheart monitors which will allow much more precise estimation of physical activity.

Food and drink consumption: Using validated brief FFQs for major food groups and also alcohol developed by our group for use in primary care. ^{31,32}

Indices of the metabolic syndrome (waist,BP,glucose,TG,HDL)³³⁻³⁶. Individuals with the metabolic syndrome are at particular risk. We will report the number (%) in each group using a definition of 3 out of 5 of high measurements³⁷, and a continuous outcome based on the mean z score for each individual (or mean rank as appropriate) - supported by empirical evidence of a close factor structure among the variables³⁸;

Waist: nurses will measure waist midway between the lower ribs and the iliac crests³⁹ also height, hip, skin fold thickness – to allow estimation of BMI, waist hip ratio, and fat mass ^{40; 41}

Blood pressure (BP) 42: Measured 3 times (after 5 min) using a validated OMRON 43;44;

Serum measures: Liver function tests (particularly to monitor non alcoholic fatty liver disease), fasting serum cholesterol/HDL/LDL/triglyceride (TG) ^{41,45,46} ⁴⁷ glucose, HbA1c and insulin ^{48,49} (which would be expected to be modified by weight reduction); also ferritin (important to measure due to reducing cereals (a key source of iron) in the low carbohydrate diet)

Patient satisfaction and understanding. Simple Likert scale responses are reliable and valid.⁵⁹; **SF36**⁵⁰: The eight scales have been shown to be valid in a wide range of conditions in primary care; **EuroQol**^{51;52} (EQ-5D): the EuroQol provides a measure of quality of life for economic analysis;

Psychological status: Using the Hospital Anxiety and Depression scale⁵⁰ and brief state anxiety.⁵³ Obesity is associated with psychological morbidity,⁵⁴ and distress, anxiety and depression may be changed by physical activity⁵⁵;

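### The blinded 12-month assessment covers only weight, leaving tape-measured waist to practice nurses who know the allocation; the same blinded staff could also measure waist

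*Protocol*

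**What the plan says.** The Outcome measurement paragraph puts the physical measurements with the practice: "At the appointments with the practice nurse (baseline, 6 months, 12 months), the physiological measurements will be performed, and patients weighed". It then adds one blinded element: "research staff blind to group will also perform a final weight measurement at 12 months". The detailed outline of recruitment and participation in Phase 2 agrees, giving the 12-month step as "Appointment made with practice nurse, validation of final weight by research nurse". No other blinded measurement is named.

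Under Secondary outcome measures, "nurses will measure waist midway between the lower ribs and the iliac crests", and the same sentence continues with "also height, hip, skin fold thickness". Waist is also one of the five components of the metabolic-syndrome outcomes (a count of patients with at least three of five high values, and a mean z score). Table 1 schedules waist and body fat at baseline, 6 and 12 months in all three arms. It lists neither hip nor skinfold.

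The practice knows the allocation. Randomisation and informed consent says "Practice staff will inform patients of their group indicating the nature and timing of contacts", and the participation outline says "Research team contacts participant and practice to inform them of allocation". The practice nurse gives the control-arm advice. For web plus nurse support, the Nurse support text says "In addition all patients will be offered brief face to face behavioural assessments at 2 weeks, 6 weeks, and 3 months", with up to four further appointments for patients not losing enough weight.

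**The concern.** The sponsor saw a need for blinded assessment and arranged staff to provide it, then applied it only to the measurement least open to the observer. A digital scale leaves little room for expectation. A tape reading depends on where the tape lies and how tightly it is pulled.

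A reading error that is the same in every arm only adds noise. One that differs by arm shifts the estimated treatment effect and does not shrink as the sample grows. A nurse who has coached a patient for months may expect a smaller waist. The outcome at stake is 12-month waist, with a small carry-over to the metabolic-syndrome outcomes. This is a matter of trial conduct that the protocol itself fixes, and no later analysis can restore blinding.

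**Working it through.** The protocol gives no figure to reproduce here. The check is mainly a reading of who measures what, followed by an illustration of size.

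**Who measures, and what they know**

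- Weight at 12 months: practice nurse, plus blinded research staff, on an automated scale.
- Waist at 12 months: nurses, at the practice-nurse appointment, by tape. No blinded assessor is named.
- Blood pressure: validated automated monitor. Serum measures: laboratory. Both depend little on the observer.
- Body fat: the protocol says the Tanita scales also allow body composition to be measured, so there is a route that needs no calipers.
- Knowledge of group: the practice is informed, by two separate statements.
- Separation of supporter and measurer: none stated.
- Baseline: the participation outline places it before randomisation, so the exposure is at follow-up only.

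**Illustration for waist**

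Inputs: n = 174 per arm with complete data (Sample size). Assumed, because the documents give no values: SD of waist change 6 to 8 cm, a differential reading shift b of 0.5 or 1 cm, no true effect, and a two-sided 5% test.

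SE of the difference = SD × √(2/174) = SD × 0.1072

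False-positive rate = P(|Z + b/SE| > 1.96)

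- SD 6 cm: SE 0.643. For b = 0.5, b/SE = 0.777 and the rate is 12.2%. For b = 1, it is 34.3%.
- SD 7 cm: SE 0.750. For b = 0.5, b/SE = 0.666 and the rate is 10.2%. For b = 1, it is 26.6%.
- SD 8 cm: SE 0.858. For b = 0.5, b/SE = 0.583 and the rate is 9.0%. For b = 1, it is 21.4%.

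In SD units, b = 0.5 cm is 0.5/8 = 0.063 to 0.5/6 = 0.083 SD. Shifts of 0.05 and 0.10 SD give 7.5% and 15% at the 5% level. At the 0.017 level that the protocol sets for weight, they give 3% and 7%.

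**Carry-over to the metabolic-syndrome z score**

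Waist is one of five inputs. Assume a cross-sectional waist SD of 10 to 14 cm. A 1 cm shift then moves the mean z score by (1/10)/5 = 0.020 to (1/14)/5 = 0.014, and a 0.5 cm shift moves it by half of that. The waist false-positive rates above do not apply to this outcome.

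**The case against.** Using limited blinded contact for the primary outcome is a defensible pragmatic choice, and nothing in the protocol is contradictory on this point. That stands, and it makes this an improvement to a secondary outcome rather than an error.

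A reader might go further than the documents allow in four ways.

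- **That the nurse who supports a patient also measures that patient.** The protocol does not say so. It gives both tasks to the same role, tells the practice the allocation and requires no separation. That is enough for a risk, not for a demonstrated bias.
- **That both web arms are favoured.** The minimal-support arm has one short face-to-face consultation, online contacts and up to two telephone calls, and controls also receive nurse advice. The plausible direction is towards web plus nurse support, and even that is an inference.
- **That hip, skinfold and fat mass are equally exposed at 12 months.** The general timing statement over the outcome list would cover hip and skinfold, but Table 1 omits both, so their collection at 12 months is unsettled. Fat mass can come from the scales.
- **That the metabolic-syndrome results share the waist error rates.** They do not: four of the five inputs come from the laboratory or an automated monitor. The three-of-five count can change only for patients close to the waist cut-off whose other components leave them at the threshold.

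It is also fair that the size of the shift and the SD of waist change are assumptions, and that the remedy leaves the 6-month readings with the nurse. Patients know their group and could disclose it, so a blinded assessor lowers the risk without removing it.

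**Conclusion.** The point holds for 12-month waist. The protocol confines blinded assessment to weight and leaves an observer-dependent measurement with staff whose practice knows the allocation and whose role delivers the support. Bias is possible, most plausibly in favour of web plus nurse support, and its size is unknown. With 174 per arm, an SD of change of 6 to 8 cm, no true effect and a two-sided 5% test, a differential shift of 0.5 cm would give about 9 to 12% false positives. That shift and those SDs are illustrative and do not come from the documents.

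The documents do not support reading this as a threat to the main result. The 12-month weight has a blinded measurement on an automated scale, so the primary conclusion is unaffected. The change is worth making because it is cheap: the blinded staff already see the patient.

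**What to change.** Amend Outcome measurement, the waist entry under Secondary outcome measures, and the 12-month step of the participation outline so that they agree on the following.

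- The blinded research staff who take the final weight also measure waist at the same contact, and hip if the protocol confirms that hip is collected at 12 months.
- The blinded reading is the 12-month analysis value for waist. A sensitivity analysis covers patients who have only a nurse reading, so that assessors are not mixed in the main result.
- Fat mass at 12 months comes from the Tanita body composition at the blinded weighing, rather than from added calipers. This assumes that the blinded weighing uses the specified scale.
- Waist at 6 months stays with the nurse and is reported as unblinded. Because the planned analysis is repeated-measures, the 12-month contrast for waist should be shown separately.

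The cost is a few minutes per patient. If it were 5 minutes (an assumption), the planned 3 × 174 = 522 completers would need 522 × 5/60 = 43.5 staff hours. Research staff need brief tape training and a tape. The change of assessor since baseline adds some noise, which should not differ by arm because baseline precedes randomisation. No extra assessor or patient contact is required.
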